- The primary endpoint is the rate of acute (within 3 months of treatment) G3+ gastrointestinal toxicities as assessed by CTCAE v4.0.

Study Design and Decision Rules

The purpose of this study is to demonstrate the feasibility of conducting a study assessing the proposed regimen. The sample size of twenty patients with confirmed resectable or borderline resectable pancreas cancer is selected based on financial and logistic considerations. However, we still propose decision rules based on testable hypotheses whenever possible. If, at the conclusion of the trial, none of the following stopping rules has been crossed, we will conclude that the proposed regimen and trial design warrants further phase II study for assessing SBRT followed by surgery in this disease population.

Accrual stopping rules

If, 4 months following the date IRB approval is obtained, no patients have been accrued, we will conclude the study does not demonstrate sufficient feasibility. Thereafter, the accrual rate will be monitored bi-monthly. If at any evaluation time point, the accrual rate is less than 0.5 per month, we will conclude the study does not demonstrate sufficient feasibility.

Toxicity Stopping Rules

The toxicity feasibility stopping rules are specified as the following:

- The toxicity rate is defined as the proportion of treated patients with resectable and/or borderline resectable pancreas cancer who experience at least one grade 3+ adverse event, and is considered at least possibly related to the preoperative treatment (i.e. an adverse event with attribute specified as “possibly,” “probably,” or “definitely” related to SBRT). The toxicity rate will be evaluated when the first 10, the first 15 and then 20 patients are enrolled and the toxicity data are available.
 - When toxicity data are available on the first 10 evaluable patients, if the toxicity rate is greater than 0.54 (> 5 patients experienced defined AEs), we will conclude the study does not demonstrate sufficient feasibility. Otherwise, continue accrual.
 - When toxicity data are available on the first 15 evaluable patients, if the toxicity rate is greater than 0.46 (> 6 patients experience defined AEs), we will conclude the study does not demonstrate sufficient feasibility. Otherwise, continue accrual.

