 - When toxicity data are available on all 20 evaluable patients, if the toxicity rate is greater than 0.42 (>8 patients experience defined AEs), we will conclude the study does not demonstrate sufficient feasibility.
 - This decision rule based on a sample size of 20 patients will have more than 80% chance to conclude the study does not demonstrate sufficient feasibility if the toxicity rate is $\geq 50\%$ and only have less than 17% chance to conclude the study does not demonstrate sufficient feasibility if the toxicity rate is $\leq 30\%$.
 - If 4 or more patients in the first 10, or after 10 patients, 40% or more treated patients experience treatment delay (> 4 weeks), we will conclude the study does not demonstrate sufficient feasibility.

Completion of Therapy Stopping Rules

The completion of therapy stopping rules are specified as the following:

- If at least 6 patients among 20 evaluable patients complete all preoperative and operative therapy including R0 or R1 resection, we will conclude the study warrants further phase II study, provided that none of the other feasibility stopping rules are crossed at any time.
- If 5 or less than 5 patients among 20 evaluable patients complete all preoperative and operative therapy we will conclude that the study does not demonstrate sufficient feasibility.
 - This decision rule based on a sample size of 20 patients will have more than 80% chance to conclude the study does not demonstrate sufficient feasibility if the R0/R1 resection rate is $\leq 20\%$ and only have less than 13% chance to conclude the study does not demonstrate sufficient feasibility if the R0/R1 resection rate is $\geq 40\%$.

Analysis Plan

All acute AE (within 3 months after treatment) and the maximum grade for each type of adverse events (including all adverse events and those that are possibly, probably or definitely related to study treatments) will be recorded for each patient. The frequency tables will be reviewed to determine the patterns. Point estimate and confidence interval will be reported for binary endpoints.

Supplementary Analysis Plans (Secondary Endpoints)

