All late AE and the maximum grade for each type of adverse events (including all adverse events and those that are possibly, probably or definitely related to study treatments) will be recorded for each patient. The frequency tables will be reviewed to determine the patterns. Point estimate and confidence interval will be reported for binary endpoints. All patients meeting the eligibility criteria and confirmed by central review who have signed a consent form and have begun any dose of treatment will be evaluable for the following secondary endpoints, unless otherwise specified.

- The positive margin resection rate is defined as number of patients achieved R0 versus R1/R2 resection during surgery divided by number of evaluable patients. (R0= negative margin, R1= microscopically positive margin, R2= macroscopically positive margin). Point estimate and confidence interval of the rate will be reported.
- The histopathologic response rate is defined as number of patients achieved CR or PR determined according to histopathologic examination during pre-operative chemo or chemoradiotherapy divided by number of evaluable patients. Point estimate and confidence interval of the rate will be reported.
- Time to locoregional recurrence is defined as time from the date of registration to the date of the first documented locoregional recurrence. The Kaplan-Meier methods will be used to estimate the median time, and event-free rate at specific time points (6 month, 12 month, etc.).
- Time to distant recurrence is defined as time from the date of registration to the date of the first documented distant recurrence. The Kaplan-Meier methods will be used to estimate the median time, and event-free rate at specific time points (6 month, 12 month, etc.).
- Overall survival is defined as time from the date of registration to the date of the death due to all causes. The Kaplan-Meier methods will be used to estimate the median time, and event-free rate at specific time points (6 month, 12 month, etc.).

Safety Stopping Rules

In addition to toxicity feasibility stopping rules, accrual will be temporarily suspended to the study, if at any time, we observe events considered at least possibly related to study treatment an adverse event with attribute specified as ("possible," "probably," or "definite") that meet the following:

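### The completion no-go bullet omits the R0/R1 condition that the go bullet and the stated error rates carry, so the two bullets are not complements as worded

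*Combined protocol and SAP*

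**What the plan says.** Section IX, Completion of Therapy Stopping Rules, has two bullets and a note on error rates.

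- Go: "If at least 6 patients among 20 evaluable patients complete all preoperative and operative therapy including R0 or R1 resection", the study warrants phase II, provided that no other feasibility rule is crossed at any time.
- No-go: "If 5 or less than 5 patients among 20 evaluable patients complete all preoperative and operative therapy we will conclude" that feasibility is not sufficient. Resection status is not mentioned.
- Error rates, placed under the no-go bullet: "This decision rule based on a sample size of 20 patients will have more than 80% chance" of a no-go verdict when the R0/R1 resection rate is 20% or lower, and less than a 13% chance when that rate is 40% or higher.

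Two other places in Section IX bear on this. Study Design and Decision Rules gives a general default: if "none of the following stopping rules has been crossed, we will conclude that the proposed regimen and trial design warrants further phase II study". Supplementary Analysis Plans lists a third surgical outcome apart from R0 and R1: "R2= macroscopically positive margin".

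**The concern.** The two bullets use complementary cut-offs (6 or more, 5 or fewer) but, as worded, different counts. The go bullet counts completers who had an R0 or R1 resection. The no-go bullet counts completers, and the plan does not say whether a patient with an R2 resection, or one explored without resection, is a completer.

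If R2 patients are completers, some results meet neither bullet. The general default and the specific go requirement then point in different directions. Completion of therapy is one of the three considerations that the Study Overview names for the phase II decision, so the verdict in that region should not have to be settled after the data are seen. The stated chance of more than 80% of rejecting a 20% R0/R1 rate would also no longer describe the rule as worded.

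**Working it through.** **Inputs.** From Section IX: n = 20; no-go at 5 or fewer, go at 6 or more; R0/R1 rates of 20% (unacceptable) and 40% (acceptable); stated no-go chances of more than 80% and less than 13%. Not in the documents, so assumed: e, the share of all patients who complete therapy with an R2 resection and are counted as completers.

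**Step 1. The plan's own figures.** Let X be the number of patients who complete with R0/R1, X ~ Binomial(20, p).

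P(no-go) = P(X ≤ 5) = Σ C(20, k) p^k (1 − p)^(20 − k), for k = 0 to 5.

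- p = 0.20: 0.0115 + 0.0576 + 0.1369 + 0.2054 + 0.2182 + 0.1746 = 0.8042. Stated: more than 80%.
- p = 0.40: 0.0000 + 0.0005 + 0.0031 + 0.0123 + 0.0350 + 0.0746 = 0.1256 (from unrounded terms). Stated: less than 13%.

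Both reproduce when the no-go count is R0/R1 completers. At 20% the slack is 80.4 − 80 = 0.4 percentage points.

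**Step 2. A result that meets neither bullet.** Take 5 R0/R1 and 1 R2 among 20, with the R2 patient counted as a completer.

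| Provision | Count used | Value | Met? |
|---|---|---|---|
| Go bullet (6 or more) | completers with R0/R1 | 5 | No |
| No-go bullet (5 or fewer), literal | completers | 6 | No |
| General default (no stopping rule crossed) | – | – | Literally yes, if nothing else is crossed |

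The default says that phase II is warranted; the go bullet's condition for saying so has failed.

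**Step 3. Literal no-go chance at an R0/R1 rate of 20%.** Completers Y ~ Binomial(20, 0.20 + e), and P(no-go) = P(Y ≤ 5). Because Y ≤ 5 implies X ≤ 5, the chance that neither bullet applies is P(X ≤ 5) − P(Y ≤ 5).

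| Assumed e | Completion rate | P(no-go), literal | Neither bullet |
|---|---|---|---|
| 0% | 20% | 80.4% | 0% |
| 2% | 22% | 73.4% | 80.4 − 73.4 = 7.0% |
| 5% (illustrative) | 25% | 61.7% | 80.4 − 61.7 = 18.7% |
| 10% (illustrative) | 30% | 41.6% | 80.4 − 41.6 = 38.8% |

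P(Y ≤ 5) falls to 80% at a completion rate of 20.13%, so an R2 share of about 0.13% uses up the slack.

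**Step 4. Literal no-go chance at an R0/R1 rate of 40%.** With e = 5% the completion rate is 45% and P(Y ≤ 5) = 5.5%, below the stated 13%. Only the figure of more than 80% is at risk from the literal reading.

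**The case against.** The strongest reply is that the section already shows what is meant. The cut-offs are exact complements, which makes sense only for a single count. The note on error rates speaks of one decision rule and gives its no-go chance in terms of the R0/R1 rate. The stated figures reproduce on that count. The no-go bullet also repeats the completion phrase that the go bullet has just tied to an R0 or R1 resection. All of this stands, and it is why the gap is best read as a drafting omission. It does not remove the gap: the qualifier appears in one bullet and not in the other, and completion is not defined elsewhere.

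Two stronger readings are tempting, and the documents support neither.

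- A reader might infer that the no-go bullet counts any completed operation. It does not say so. It leaves out the R0/R1 condition, still requires all preoperative therapy, and is silent on R2 and on exploration without resection.
- A reader might infer that a trial with fewer than six R0/R1 resections receives a go verdict by default. That requires the general sentence to override the specific go requirement, and nothing in Section IX gives it precedence. The text yields a conflict, not a settled go.

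The size is also open to challenge. At an R0/R1 rate of 20%, e = 5% means that 5/25, or one fifth, of resections are R2, and e = 10% means 10/30, or one third. The only margin result after SBRT in the documents is a 90% negative-margin rate among resected patients, in the Rationale and cited there as a personal communication. If every other margin in such a series were R2, then with 20% R0/R1 taken as the 90%, resections would be 0.20/0.90 = 22.2% of patients and e about 2.2%, giving a literal no-go chance of 72.6%. That is close to the 2% row. The 5% and 10% rows have no support in the documents.

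Finally, completion is not the primary endpoint, and this rule is stated only for 20 evaluable patients, so the omission does not touch interim safety monitoring.

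**Conclusion.** The point holds as a minor wording error. Read literally, the go and no-go bullets are not complements. If an R2 resection counts as completed operative therapy, results such as 5 R0/R1 plus 1 R2 have no verdict under the completion rule and set the general default against the go requirement.

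The plan's error rates are correct for an R0/R1 count (80.4% and 12.6%). Under the literal wording, any R2 share above about 0.13% takes the first figure below 80%; an assumed 2% share gives 73.4%, with a 7.0% chance that neither bullet applies. These sizes rest on an R0/R1 rate of exactly 20%, independent patients, 20 evaluable patients, and an R2 share that the documents do not give. The wording gap itself depends on none of these assumptions.

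**What to change.** In Section IX, Completion of Therapy Stopping Rules, carry the go bullet's R0/R1 condition into the no-go bullet, so that both bullets count patients who complete all preoperative and operative therapy with an R0 or R1 resection. Add one sentence: for this rule, an evaluable patient without an R0 or R1 resection, whether the operation was an R2 resection or an exploration without resection, counts as a non-completer.

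The bullets then become complements, the general default agrees with the go requirement, and the stated figures apply to the rule as written. The cost is a few words in one section. Thresholds, sample size, stated probabilities and study procedures stay as they are.

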SECONDARY OBJECTIVES	To evaluate rates of late (> 3 months after treatment) gastrointestinal toxicity following fractionated Linac based SBRT for pancreatic tumors. Toxicities of note include grade 2 or greater gastritis, enteritis, fistula, or ulcer and any other grade 3 or greater gastrointestinal toxicity. To evaluate local progression free survival, overall survival and metastasis-free survival rates after Linac based SBRT and subsequent resection in patients with resectable and/or borderline resectable pancreatic adenocarcinoma of the head and/or body. To develop and standardize Linac based SBRT delivery and dosimetric parameters. To estimate resection margin positivity (R0/R1) and pathologic complete response rate after neoadjuvant SBRT To evaluate pre- and post- SBRT patient reported quality of life (QOL)
TREATMENT	After 3- 4 months of chemotherapy, patients will be enrolled to a single arm trial of stereotactic body radiotherapy (SBRT) in 5 fractions given over 15 days. They will then proceed to surgery after a break of 4-6 weeks.

INCLUSION CRITERIA	
 • Age >18 years. • Karnofsky Performance Status >70% (see Appendix IV). • Histologically confirmed pancreatic adenocarcinoma of the head and/or body; at least the majority of the histopathologic specimen must be identified as adenocarcinoma. • Pancreatic tumors must be considered at least borderline resectable and/or borderline resectable at time of treatment planning. Definition of resectable and/or borderline resectable: no metastases, less than 180 degree involvement of hepatic artery, superior mesenteric artery or celiac artery • No active infection requiring hospitalization • If bilirubin > 2, patients must have a biliary stent placed prior to SBRT. • Patients must have acceptable organ and marrow function (see section “Inclusion Criteria, page 17-18). • Women who are not post-menopausal (as defined in Appendix V) should have a negative urine or serum pregnancy test. Women of childbearing potential must agree to use adequate contraception for the duration of study participation. • Ability to understand and the willingness to sign a written informed consent document. • Life expectancy > 3 months. • Patients are to have received neoadjuvant chemotherapy prior to enrollment. Approved regimens may consist of 3-4 months of gemcitabine-based chemotherapy or FOLFIRINOX. Patients will have a 2-4 week break between last chemotherapy administration and start of

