Koong et al. previously used the Cyberknife™ stereotactic radiosurgery system to demonstrate that a single dose of 25 Gy Linac based stereotactic body radiotherapy (SBRT) was feasible for patients with locally advanced pancreatic cancer (36). Furthermore, this dose of radiation resulted in near 100% progression free survival and effectively palliated symptoms related to the local growth of pancreatic tumors. Based on this study, the same group also completed a phase II study assessing the efficacy of combining a standard five- week course of chemoradiotherapy followed by a stereotactic radiosurgery boost to the primary tumor in patients with locally advanced pancreatic cancer. In this cohort of 19 patients, 100% of tumors were without local progression at 1 year median follow-up. However, all patients eventually developed metastases..

More recently, another phase II study treated locally advanced pancreatic cancer patients with gemcitabine followed by 25 Gy of Linac based SBRT delivered with Cyberknife and maintenance gemcitabine chemotherapy. In this study, the excellent progression free survival was confirmed from previous studies (81%). The median overall survival was 11.4 months, median time to progression was 9.7 months and the 1 year survival was 50% (37). There were no significant acute GI toxicities however, of the 15 patients alive >6 months after Linac based SBRT, 7 (47%) experienced Grade 2 or greater GI toxicity, with 2 (13%) of the 15 experiencing Grade 3 or greater GI toxicity.

A multi-institutional study (Johns Hopkins, Stanford, Memorial Sloan Kettering) of fractionated SBRT (6.6Gy x 5) in 70 patients with locally advanced or borderline resectable and/or borderline resectable pancreatic adenocarcinoma has thus far shown very promising results. Median overall survival of the locally advanced patients was 13.9 mo (comparable to national standard) with 83% local control at 1 year. Furthermore, patients reported improved global and pancreas specific

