Based upon prior phase I and phase II studies evaluating the toxicities associated with Linac based SBRT for pancreatic cancer, we estimate that $\leq 20\%$ of patients will experience grade 2 or higher late GI toxicity within one year. Late GI toxicities are those events occurring more than 3 months after Linac based SBRT. Acute GI toxicities are those events occurring within 3 months following Linac based SBRT. The major toxicity in this group of patients is the development of duodenal/gastric ulcers. Most of these are successfully managed medically. However, Stanford has observed 2 cases of duodenal perforation associated with Linac based SBRT in patients who did not undergo surgical resection of their tumors. We anticipate that because of refinements in radiation treatment planning techniques and because the dose will be divided over five treatments (as opposed to one), the biological equivalent and actual dose to the duodenum will be less than prior studies. Furthermore, the Stanford observed perforations occurred in duodenal locations that are routinely removed with pancreaticoduodenectomy, and all of our patients are anticipated to go to surgery. We anticipate that the risk of ulcer formation should be low ($< 5\%$) in this study. Hepatic and renal toxicity is not anticipated given the expectation of limited incidental irradiation of these organs.

Reporting of Serious or Unexpected Adverse Events

All fatal events, both anticipated and unanticipated, must be reported to the UC IRB within a time period as specified by current institutional guidelines after the PI learns of the event, whether or

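### Late GI toxicity is planned as a simple proportion with no time horizon, at-risk set or rule for death and loss, so it cannot be read against the protocol's one-year expectation

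*Combined protocol and SAP*

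**What the plan says.** The synopsis lists as a secondary objective "To evaluate rates of late (> 3 months after treatment) gastrointestinal toxicity following fractionated Linac based SBRT for pancreatic tumors". Section VIII repeats the window: "Late GI toxicities are those events occurring more than 3 months after Linac based SBRT". Neither gives an upper limit.

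The analysis is in Section IX, Supplementary Analysis Plans (Secondary Endpoints). What is recorded is "All late AE and the maximum grade for each type of adverse events", per patient. Then "The frequency tables will be reviewed to determine the patterns", and finally "Point estimate and confidence interval will be reported for binary endpoints". Nothing more is said about late toxicity.

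The sentence defining the evaluable set comes after this text. It covers eligible, consented patients who "have begun any dose of treatment will be evaluable for the following secondary endpoints, unless otherwise specified". Section XII adds only that patients are evaluable for toxicity at the follow-up visits. In the same part of Section IX, time to locoregional recurrence, time to distant recurrence and overall survival are all given Kaplan-Meier estimates at 6 months, 12 months and so on.

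Two reference figures appear. Section VIII expects that at most 20% "of patients will experience grade 2 or higher late GI toxicity within one year". Section III, on the earlier single-fraction 25 Gy study, reports that "of the 15 patients alive >6 months after Linac based SBRT, 7 (47%) experienced Grade 2 or greater GI toxicity".

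**The concern.** A late event can be seen only in a patient who is alive and under observation after month 3, and the chance of seeing one grows with time observed. Section VI allows follow-up of up to 5 years, expects about one year for most patients, and plans 24 months of accrual plus 12 of maturation. Observation time would therefore differ between patients even if nobody died.

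A simple proportion gives a patient lost at month 5 the same weight as one followed for 5 years. It also leaves open whether a patient who dies at month 2 is in the denominator. The result has no time attached to it, while the protocol's own expectation is tied to one year. What is at stake is whether the late-toxicity figure from this trial can be interpreted or carried into the planning of a later study.

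**Working it through.** **The documents' own figure.** 7/15 = 46.7%, which reproduces the stated 47% (exact 95% CI 21.3-73.4%). No assumed late rate enters a sample-size calculation: the 20 patients are chosen on financial and logistic grounds.

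**Effect of the denominator alone.** Four events are 4/20 = 20.0% of all treated patients (exact 95% CI 5.7-43.7%), but 4/14 = 28.6% if only 14 patients alive at 6 months are counted (8.4-58.1%).

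**Effect of the horizon: inputs.**
- Median survival m = 8 and 23 months: the range for neoadjuvant series in Section II. m = 11.4 months: the earlier SBRT study in Section III.
- Risk of late toxicity by month 12 if nobody died: 20%. This is an assumption, borrowed from the size of the Section VIII expectation.
- Constant hazard of death from SBRT, and constant hazard of late toxicity from month 3. Both are assumptions.

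**Formulas.** Death hazard μ = ln 2 / m. Toxicity hazard λ = −ln(1 − 0.20)/9 = 0.02479 per month. Proportion of all treated patients with a late event by month T:

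P(T) = exp(−3μ) × λ/(λ+μ) × [1 − exp(−(λ+μ)(T − 3))]

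**Results.**

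| Median survival | μ | Alive at 3 months, of 20 | λ/(λ+μ) | P(12), all treated | P(12), of those alive at 3 months | P(60), all treated |
|---|---|---|---|---|---|---|
| 8 months | 0.0866 | 15.4 | 0.222 | 10.9% | 14.1% | 17.1% |
| 11.4 months | 0.0608 | 16.7 | 0.290 | 13.0% | 15.6% | 24.0% |
| 23 months | 0.0301 | 18.3 | 0.451 | 16.1% | 17.6% | 39.4% |

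Worked line for m = 11.4: exp(−0.1824) = 0.833; 1 − exp(−0.0856 × 9) = 0.537; 0.833 × 0.290 × 0.537 = 13.0%. With T = 60 the last factor becomes 1 − exp(−0.0856 × 57) = 0.992, and 0.833 × 0.290 × 0.992 = 24.0%.

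**Other survival inputs.** Medians of 12 months (the 50% one-year survival in Section III), 13.9 months (Section III) and 20 months (assumed) give 13.2%, 14.0% and 15.6% counted to month 12, and 25.0%, 28.2% and 36.3% counted to month 60.

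One underlying risk thus gives figures on either side of 20%, depending only on when counting stops and how long patients live.

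**The case against.** The strongest reply is that this is a descriptive secondary endpoint in a 20-patient pilot. The 20% is an expectation in a risk list, not a threshold, and no accrual, toxicity, completion or safety rule uses it. Any interval will be wide: with 23-month median survival, the gap between 20% and 16.1% is 3.9 points, or 0.8 of a patient in 20. All of that stands and limits the weight of the point.

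A reader might go further and infer that early deaths bias the late rate downwards, so that a too-toxic regimen could appear to meet the 20%. The documents do not support that, for three reasons.
- The dilution appears only with a 12-month cut-off, which the plan does not contain. With the window left open, the proportion in most of the scenarios above exceeds 20%.
- The all-treated denominator is an inference. The any-dose evaluable set is stated for the endpoints listed after it, and late events are described before it.
- The Section VIII figure is a share of patients, with no condition on survival. If follow-up to 12 months were complete, the crude proportion over all treated patients counted to month 12 would equal the cumulative incidence with death competing. Mortality would then cause no bias against that figure; only loss to follow-up would.

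A reader might also fault the comparison with the earlier 47%. No such comparison is planned, and restricting to patients alive beyond 6 months would not make it like with like. The earlier regimen was a single fraction, and its figure counts any grade 2 or greater GI toxicity. This trial's objective counts grade 2 or greater only for gastritis, enteritis, fistula and ulcer, and grade 3 or greater otherwise. The 47% is context only.

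Finally, constant hazards out to 60 months are an assumption, and 60 months is the longest follow-up allowed. The upper figures mark an outer range, not a forecast.

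**Conclusion.** The point holds as a gap in definition. Horizon, at-risk set and the handling of death and loss are all missing for a named secondary objective, in a disease where the documents' own survival figures make unequal follow-up certain. Taken as written, the plan yields a rate that depends on length of follow-up and cannot be read against the one-year expectation.

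The possible size is material: about 11-16% counted to 12 months against about 17-39% counted to 60 months, for the same assumed 20% one-year risk without death and median survival of 8 to 23 months, under constant hazards. The sign of the discrepancy is indeterminate, so the rate should not be called biased in either direction. The primary endpoint and the feasibility conclusions are untouched. The change is worth making because it is cheap, not because the trial's decision depends on it.

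**What to change.** In Section IX, Supplementary Analysis Plans, replace the open-ended proportion for late GI toxicity with the following:
- **Estimand:** 12-month cumulative incidence of first late GI toxicity as defined in the secondary objective, with death as a competing event and loss to follow-up censored.
- **Two populations:** all treated patients, to match the share-of-patients form of the Section VIII expectation; and a 3-month landmark in patients alive and in follow-up at that time. Define the landmark by time since SBRT rather than by visit, because Section IV lists a 3-month visit and the study calendar a 4-month one.
- **Reporting:** 95% interval and number at risk. Keep the crude proportion as a descriptive figure, with the range of follow-up beside it.
- **Reading against 20%:** the Section VIII figure covers any grade 2 or higher late GI event, which is broader than the secondary objective. State this, or tabulate that broader definition as well.

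The study calendar already schedules adverse-event evaluation at each follow-up visit, and the data list already includes toxicities and withdrawal dates. The date of the first qualifying event should be captured explicitly, because the plan mentions only the maximum grade per event type. The 12 months of maturation after accrual make a 12-month horizon workable.

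The cost is a few sentences of plan text, slightly more analysis and an interval that stays wide at 20 patients. It needs no extra patients or visits and no change to any decision rule.
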